13.5.2 Foreseeable Risk and Discomfort Related to BT063

13.5.2.1 *Potential risks*

- Uncertain effect on the mucous membrane of the gastrointestinal tract (GI)
- Hypersensitivity reactions
- Interactions with other drugs
- Interaction with live vaccines or induction of immune system overreactions in vaccinated subjects
- Infections

13.5.2.2 *Identified risks*

Based on the results of the completed Phase I study in healthy subjects the following risks were classified as identified for BT063:

- Mouth ulcers/aphthous stomatitis

13.5.2.3 *Important missing information*

- Lack of knowledge about potential influence on pregnant women and embryonic development

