Not related:	Adverse events for which a reasonable explanation for an alternative cause is considered plausible, e.g., no study drug taken, plausible clinical alternative like accidental injury, expected progression of underlying or concomitant disease, pharmacologically incompatible temporal relationship, or intercurrent illness.
Related:	Adverse events for which a reasonably possible clinical and/or pharmacological relationship to study drug cannot be excluded, e.g., lacking plausible alternatives.

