14.3.2 Recording Adverse Events

Period: Subject Enrolment to the First Administration of Study Drug: Non-treatment emergent AEs will be recorded from the time when the subject is enrolled into the study (date of signature of the informed consent) until first administration of study drug.

Period: First Administration of Study Drug to Subject's last study visit: Thereafter all AEs are treatment-emergent AEs (TEAEs, see Definitions, [Section 14.3.1](#)) and will be recorded until the final follow-up visit has been performed.

Period after last study visit: Any SAE occurring after the subject's last study visit but considered by the investigator to be related to the study drug will be recorded.

If an AE (serious or not) started during the study but did not end before the final follow-up visit, the investigator should make a reasonable effort to establish the outcome and the end date. If this is not possible, the outcome recorded at the final follow-up visit will be assumed to be the final outcome.

If an event stops and later restarts, all the occurrences must be reported. Adverse events assessed as related to study medication by the investigator and all SAEs must be followed up until resolution.

Signs/symptoms should be documented if a definite diagnosis cannot be established. The investigator should attempt to establish a diagnosis of the event based on signs, symptoms and/or other clinical information. In such cases, the diagnosis should be documented as the AE and/or SAE and not the individual signs/symptoms. If a diagnosis is accompanied by unusual symptoms, the diagnosis itself and the symptoms have to be reported separately.

In addition to the definition as given, the following special types of events should be recorded:

- a) **Pregnancy** - Although not an AE per se, occurrence of pregnancy in a subject during a clinical study must be recorded.

b) **Laboratory values that are outside the normal range** and if, in the opinion of the investigator, these values represent a clinically relevant change versus pre-treatment values are also defined as AEs.

If abnormal laboratory values are signs of an AE (e.g., an infection) that has already been recorded, the respective abnormal laboratory value does not constitute a separate AE.

Wherever reasonable the reporting investigator will use the clinical term rather than the laboratory term (e.g., anaemia versus low haemoglobin value).

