The investigator will notify [REDACTED] Drug Safety department of any SAE that she or he becomes aware of and considers related to the study drug.

Following-up AEs / SAEs:

At the subject's last study visit (including the Early Termination Visit), a Safety Follow-up Visit should be scheduled up to 2 weeks after the final examination only for those subjects who experienced not resolved related AEs or laboratory parameters showing not normalized clinical relevant changes or SAEs. The assessments measured will be determined by the investigator. All data must be documented in the eCRF.

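### The two causality categories overlap with no precedence rule, so a non-serious mouth ulcer can be classed as not related and fall outside mandatory follow-up

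*Protocol*

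**What the plan says.** Protocol Section 14.3.1 (Causality of Adverse Event) offers two categories.

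- *Not related*: "Adverse events for which a reasonable explanation for an alternative cause is considered plausible". One of the listed examples is "expected progression of underlying or concomitant disease".
- *Related*: "Adverse events for which a reasonably possible clinical and/or pharmacological relationship to study drug cannot be excluded, e.g., lacking plausible alternatives".

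Three duties refer to this label or bear on the same events.

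- Section 14.3.2: "Adverse events assessed as related to study medication by the investigator and all SAEs must be followed up until resolution". For any other event still open at the final follow-up visit, "the investigator should make a reasonable effort to establish the outcome and the end date"; failing that, the outcome noted at that visit stands as final.
- Section 14.3.4.1: a Safety Follow-up Visit, up to two weeks after the final examination, is scheduled "only for those subjects who experienced not resolved related AEs or laboratory parameters" with clinically relevant changes that have not normalised, or with serious events.
- Section 14.3.2 again: after the last study visit, serious events are recorded only if the investigator considers them related.

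Section 15.2.4 lists causal relationship among the aspects on which the further adverse event analyses will focus.

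Section 13.5.2.2 names one identified risk of BT063: "Mouth ulcers/aphthous stomatitis". Section 14.1.2.1 makes aphthous mouth ulcers an adverse event of special interest (AESI), including recurrent lesions and worsening of existing ones. Oral ulcers are also criterion 4 of the lupus classification in Appendix B, and mucosal ulcers are a SLEDAI-2K item with weight 2 in Appendix C.

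**The concern.** A two-way causality scale should place each event in exactly one category. This one asks a different question for each: whether something else could explain the event, and whether the drug can be ruled out. For the event the protocol names as the drug's identified risk, the answers will often be yes to the first and no to the second, because the disease under study also causes oral ulcers.

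Investigators can then label the same clinical picture differently, and the examples push towards *Not related*: disease progression illustrates that category, while *Related* is illustrated only by the absence of other explanations. The label decides whether a non-serious event must be followed to its end, and it feeds the analysis by relationship. The SAP cannot repair this later, because the label is assigned at the site under this definition.

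**Working it through.** The protocol states no figure on this point, so the check is logical. Take two yes/no questions, one from each definition in Section 14.3.1, and go through all four combinations.

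| Other cause plausible? | Drug relationship excluded? | Category met |
|---|---|---|
| Yes | Yes | *Not related* only |
| No | No | *Related* only |
| Yes | No | both |
| No | Yes | neither |

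The categories are neither mutually exclusive nor exhaustive. The third row is the one that matters in practice, and Section 14.3.1 has no tie-break for it.

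**Does a mouth ulcer fall in the third row?** Another cause is plausible, because the protocol's own appendices list oral ulceration as a feature of lupus. A drug relationship is hard to exclude, because the protocol lists mouth ulcers as an identified risk. Section 11.1.3 reports them in healthy subjects from the 15 mg dose group of Study 977 upward, where no lupus was available as an explanation. So the ulcer meets both definitions.

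**What follows if it is labelled *Not related*?**

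1. If it is non-serious, it is outside the Section 14.3.2 duty to follow to resolution, which covers investigator-assessed related events and serious events. AESIs are not listed there.
2. It does not by itself trigger the Safety Follow-up Visit of Section 14.3.4.1, where AESIs are again not listed.
3. It is not counted as related in the summaries under Section 15.2.4. With 12 BT063 subjects per part, one subject moves the related-event incidence by 1/12 = 8.3 percentage points, provided that subject has no other related event. This gives the scale per subject; it does not say how many subjects would be affected.

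**What does not change with the label?**

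1. All AESIs are reportable within 24 hours (Section 14.3.1).
2. The separate AESI form, with onset, resolution and outcome, is completed regardless of causality (Section 14.3.2.1).
3. Adverse events are recorded at visits through week 28 (Section 13.1). That is day 196 against a last dose on day 84, so 112 days or 16 weeks.
4. The lesser duty to try to establish outcome and end date still applies (Section 14.3.2).
5. The primary endpoint is incidence of adverse events whatever their cause (Synopsis).

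**When does the lost duty bite?** It bites when the event is still open at the subject's last visit. For completers that is week 28. For early terminators, Section 14.3.4.1 counts the Early Termination Visit as a possible last visit, and Section 12.4 places it two weeks after the last dose. Fourteen days is less than one half-life (20 to 26 days, Section 11.1.3), and the same section reports an ulcer recurrence 43 days after dosing.

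**The case against.** The strongest reply is that the text does not make such an event *Not related*. It meets *Related* equally well, the lack of alternatives is only an example there, and the disease example speaks of expected progression, not of any lupus symptom. Investigators are also told that mouth ulcers are an identified risk. This stands: the events *can be* classed as *Not related*, and nothing says that they must be.

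The second reply is that AESIs have their own safeguards. Section 14.1.2.1 describes them as warranting close monitoring, serious or not. Reporting, the form, and recording at visits through week 28 are all independent of causality, and serious ulcers are followed as serious events. This also stands and narrows what is lost to the firm duty of follow-up to resolution and one extra visit whose content the investigator chooses.

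The third reply is that the main safety comparison is of all adverse events against randomised placebo under blinding, so a drug effect on ulcers would show whatever the label. That is right for the primary endpoint. Blinding also makes systematic labelling differences between arms less likely, but it does not prevent inconsistent labels or an undercount of related events. Section 14.3.3.2 has a differing sponsor opinion recorded, yet the duty in Section 14.3.2 follows the investigator's assessment.

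A reader might infer more than the documents support:

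- *That the board choosing the Part II dose sees tables by relationship.* Section 15.2.8 mentions only descriptive safety and efficacy tables and listings, and the board's procedures are in a separate charter.
- *That the per-protocol set depends on the label.* Section 15.2.1 uses its own wording about a possible relation and does not refer to these categories.
- *That every named risk has a ready alternative cause.* Section 13.5.2.1 also lists hypersensitivity, drug interactions and vaccine interactions, for which no such explanation is evident.
- *That nearly all mouth ulcer, gastrointestinal and infection events would be relabelled.* No figure supports this. The 40% for gastrointestinal disease in Section 6 refers to the whole course of lupus.

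**Conclusion.** The overlap is real and visible on the face of Section 14.3.1. Its reach is limited: a non-serious mouth ulcer in a lupus subject can be labelled *Not related*, then carries no duty of follow-up to resolution and no Safety Follow-up Visit on its own account, and lowers the related-event summaries by up to 8.3 percentage points for each BT063 subject in a part. How often this would happen cannot be estimated from the protocol. Late serious events share the ambiguity, since they are recorded after the last visit only if considered related.

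To say that mouth ulcers would go unrecorded or unreported, or that the primary safety conclusion is compromised, would be wrong. The conclusion assumes that investigators apply the definitions as written, without a completion guideline that settles the tie; none is shown. The change is worth making because it is cheap and concerns the event of most interest for this drug.

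**What to change.** Amend the causality box in Section 14.3.1 so that one question decides, with *Related* taking precedence:

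- *Related*: a reasonable possibility that the study drug caused or contributed to the event cannot be excluded, even if lupus or background therapy is also a plausible cause.
- *Not related*: that possibility can be excluded, for example because no study drug was given or the timing is incompatible.

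State that a plausible disease explanation is not sufficient on its own for *Not related*. This also closes the gap in which an event meets neither definition. Some judgement by the investigator remains, but it is applied to a single question.

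Separately, reconcile Sections 14.1.2.1, 14.3.2 and 14.3.4.1 so that they agree on whether follow-up of AESIs depends on the causality label.

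The cost is one definition and the matching eCRF guidance in an amendment. The downside is that somewhat more events will be classed as related, with more follow-up and a less favourable related-event count. If subjects are already enrolled, events assessed under the existing wording would need reassessment or separate presentation.

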14.3.2 Recording Adverse Events

Period: Subject Enrolment to the First Administration of Study Drug: Non-treatment emergent AEs will be recorded from the time when the subject is enrolled into the study (date of signature of the informed consent) until first administration of study drug.

Period: First Administration of Study Drug to Subject's last study visit: Thereafter all AEs are treatment-emergent AEs (TEAEs, see Definitions, [Section 14.3.1](#)) and will be recorded until the final follow-up visit has been performed.

Period after last study visit: Any SAE occurring after the subject's last study visit but considered by the investigator to be related to the study drug will be recorded.

If an AE (serious or not) started during the study but did not end before the final follow-up visit, the investigator should make a reasonable effort to establish the outcome and the end date. If this is not possible, the outcome recorded at the final follow-up visit will be assumed to be the final outcome.

If an event stops and later restarts, all the occurrences must be reported. Adverse events assessed as related to study medication by the investigator and all SAEs must be followed up until resolution.

Signs/symptoms should be documented if a definite diagnosis cannot be established. The investigator should attempt to establish a diagnosis of the event based on signs, symptoms and/or other clinical information. In such cases, the diagnosis should be documented as the AE and/or SAE and not the individual signs/symptoms. If a diagnosis is accompanied by unusual symptoms, the diagnosis itself and the symptoms have to be reported separately.

In addition to the definition as given, the following special types of events should be recorded:

- a) **Pregnancy** - Although not an AE per se, occurrence of pregnancy in a subject during a clinical study must be recorded.

b) **Laboratory values that are outside the normal range** and if, in the opinion of the investigator, these values represent a clinically relevant change versus pre-treatment values are also defined as AEs.

If abnormal laboratory values are signs of an AE (e.g., an infection) that has already been recorded, the respective abnormal laboratory value does not constitute a separate AE.

Wherever reasonable the reporting investigator will use the clinical term rather than the laboratory term (e.g., anaemia versus low haemoglobin value).

14.3.2.1 Responsibilities of Investigator

Adverse event data should be obtained through observation of the subject, from any information volunteered by the subject, or through subject questioning. The general type of question asked could be similar to: "Do you have any health problems?" or "Have you had any health problems since your last clinic visit?"

Adverse events are to be recorded accurately and completely on the AE pages of the respective CRF and in the subject's source data.

All non-treatment and treatment-emergent AEs will be recorded.

This is true even if the IMP was not administered according to the study protocol.

For conditions leading to unplanned surgical procedures the underlying condition, should be documented as an AE, but not the procedure.

Reporting IRAEs:

For AEs that are "serious" (SAEs) and AESIs ([Section 14.1.2.1](#) additional separate documentation is required using the electronic SAE/AESI Forms.

The following variables will be recorded on the electronic SAE/AESI Form and on the eCRFs provided in accordance to the eCRF completion guidelines:

- Description of the event, including its duration (date of onset and resolution),
- Whether the event constitutes a SAE/AESI or not (if yes, see event seriousness criteria in [Section 14.3.1](#))
- Any action taken (e.g., *changes to study treatment, other treatment given and follow up tests*)
- Outcome of the event
- Investigator's assessment of causality (*the relationship to the study treatment[s] and study procedures*)
- Severity.

For all SAEs where important or relevant information is missing, follow-up should be undertaken to ensure that all information is reported.

Whether or not a causal relationship exists between the study medication/study conduct and the AE is not relevant. The investigator is obligated to record AEs and notifying IRAEs to the Sponsor.

For withdrawals due to AEs the eCRF page "Study completion / Study termination Form" and a copy of the eCRF AE page needs to be completed and forwarded to [REDACTED] Drug Safety Department.

Pregnancy Reporting: Each pregnancy that starts during the study must be reported by the investigator to [REDACTED] Drug Safety Department within 24 hours of the investigator's knowledge of the pregnancy by using the SAE Form. Any adverse outcome of the pregnancy must be recorded and notified on the "Drug Exposure via Parent Report Form". The investigator should make any reasonable effort to follow any pregnancy until birth of the child.

Overdose (as defined in [Section 11.1.4](#)) needs to be reported to [REDACTED] Drug Safety Department following the criteria for SAE reporting.

If additional information is required by the [REDACTED] Drug Safety department, then as a representative of the Sponsor [REDACTED] must be granted access to the medical records.

After subject's last study visit:

The investigator records and forwards to the Sponsor all SAEs that she or he becomes aware of and she or he considers related to the IMP.

14.3.2.2 Responsibilities of Sponsor

For purposes of safety analyses all AEs will be recorded in the clinical database. To ensure expedited and periodic notification of authorities, SAEs will also be recorded in the drug safety database.

14.3.3 Evaluation of Adverse Events

14.3.3.1 Responsibilities of Investigator

The investigator will assess the seriousness, severity, and causality of each AE in accordance with the definitions in [Section 14.3.1](#). Notification of IraEs must follow the procedure described in [Section 14.3.2.1](#).

Causality of AE:

For all AEs a causality assessment must be provided and documented on the respective form (eCRF AE page for all AEs, SAE form for SAEs and eCRF page "Study completion / termination form" for withdrawals due to AEs).

14.3.3.2 Responsibility of Sponsor

The Sponsor will not downgrade the causality assessment provided by the investigator. If the Sponsor disagrees with the investigator's causality assessment, both the opinion of the investigator and the Sponsor will be recorded.

14.3.4 Notifying of Adverse Events

14.3.4.1 *Responsibility of Investigator*

For IRAEs (SAEs, AEs leading to withdrawal, and AESIs) the investigator must inform the [REDACTED] Drug Safety department via e-mail or fax using the SAE report/eCRF page within 24 hours of the study site being informed of the IRAE. At a later date, the [REDACTED] Safety Contact will report to Biostest Corporate Drug Safety, the Clinical Study Manager, and the Clinical Research Physician.

Adverse Event Reporting Contact:

[REDACTED] Drug Safety

E-mail: [REDACTED]

Fax: [REDACTED]

For questions regarding IRAEs, or to provide information that cannot be provided electronically, or to notify the Sponsor of an IRAE in the event of technical failure, the investigator should contact [REDACTED]

Investigators or other site personnel should inform [REDACTED] Drug Safety department of any follow-up information that becomes available for a previously reported SAE immediately but no later than 24 hours of becoming aware of the information. Follow-up reports (as many as required) should be completed and faxed or e-mailed following the same procedure above. Any requested supporting documentation (e.g., ECG, laboratory results, autopsy report) should be sent to the [REDACTED] Drug Safety department.

Prior to forwarding any personal data for safety reporting, the documents need to be coded in a way that keeps the subject's identity confidential (e.g., by using the subject's identification code, randomization number, etc.).

For fatal and life-threatening SAEs, [REDACTED] Drug Safety department will work with the investigator to ensure that any additional information is provided by the investigator within 1 business day. The investigator will ensure that all the necessary information for all other SAEs will be provided within the timelines stipulated by the Sponsor when the request for information is made.

If required, the investigator is responsible for informing local IECs/IRBs of safety reports in compliance with applicable regulatory requirements. Copies of all correspondence relating to reporting of any safety reports to the IEC/IRB should be maintained in the ISF / Regulatory Binder.

Subject Enrolment to the First Administration of Study Drug:

Only serious procedure-related AEs will be reported to the Sponsor using the IRAE reporting process (SAE report form) as described above.

After subject's last study visit:

The investigator will notify [REDACTED] Drug Safety department of any SAE that she or he becomes aware of and considers related to the study drug.

Following-up AEs / SAEs:

At the subject's last study visit (including the Early Termination Visit), a Safety Follow-up Visit should be scheduled up to 2 weeks after the final examination only for those subjects who experienced not resolved related AEs or laboratory parameters showing not normalized clinical relevant changes or SAEs. The assessments measured will be determined by the investigator. All data must be documented in the eCRF.

14.3.4.2 Responsibility of Sponsor

Bioteest's Corporate Drug Safety department is responsible for fulfilling all obligations regarding notification of Regulatory Authorities and IECs/IRBs according to applicable regulatory requirements (expedited and periodic reporting, e.g., serious unexpected suspected adverse reactions, Development Safety Update Report). In addition, the Sponsor will provide safety information to investigators according to the current regulations.

